- Pregnancy and Nursing Mothers: [Note: females of child-bearing potential as well as pregnant and/or nursing mothers are excluded from participation in this study.] Corticosteroids have been shown to be teratogenic in laboratory animals when administered systemically at relatively low dosage levels (Pregnancy Category C). When administered subcutaneously, CP was a significant teratogen in both the rabbit and mouse.

Systemically administered corticosteroids appear in human milk and could suppress growth, interfere with endogenous corticosteroid production, or cause other untoward effects. It is not known whether ocular administration of APP13007 could result in sufficient systemic absorption of CP to produce detectable concentrations in human milk.

[REDACTED] plasma CP concentrations in human subjects after ocular instillation of one drop of APP13007 are expected to be lower than that observed in human subjects after dermal application of CP-containing products.

Potential ocular risks are summarized below.

Potential Class-Related Ocular Risks Associated with Corticosteroid Therapies for the Treatment of Ocular Inflammation and Pain after Ocular Surgery

[figure not shown]
The active ingredient in APP13007, [REDACTED] has the following anticipated ocular risks associated with the corticosteroid class:

- Intraocular pressure (IOP) increase – prolonged use may result in glaucoma with damage to the optic nerve, defects in visual acuity and field of vision.
- Cataracts – Prolonged use [REDACTED] may result in posterior subcapsular cataract formation in the non-operated eye.
- Delayed healing – Use [REDACTED] after cataract surgery may delay healing and increase the incidence of bleb formation. In those diseases causing thinning of the cornea or sclera, perforations have been known to occur with the use of topical corticosteroids.
- Risk of Infection
 - Bacterial infections – Prolonged use [REDACTED] may suppress the host immune response and thus increase the hazard of secondary ocular infections. In acute purulent conditions, corticosteroids may mask infection or enhance existing infection.
 - Viral infections – Use of ocular corticosteroids may prolong the course and may exacerbate the severity of many viral infections of the eye (including herpes simplex).
 - Fungal Infections – Fungal infections of the cornea are particularly prone to develop coincidentally with long-term local corticosteroid application. Fungus invasion must

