1.4.1.2. Contraindications

APP13007, as with other corticosteroids, is contraindicated in the presence of active viral diseases of the cornea and conjunctiva including epithelial herpes simplex keratitis (dendritic keratitis), vaccinia, and varicella, and also in subjects with mycobacterial infection of the eye and fungal diseases of ocular structures.

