Unexpected safety events	
Safety endpoints will be monitored during the trial.
 
The Investigator will discuss unexpected safety events with the Study Medical Monitor who will then discuss unexpected safety events with the Sponsor to determine whether study drug should be stopped and rescue procedures commenced.
	
The toxicology studies with APP13007 indicate that there is a low risk of ocular toxicity. While the risks of systemic exposure to CP following dermal/topical administration are well characterized, aqueous formulations of CP have not been dosed to the human eye before.
 
Therefore, the Investigator should be alert to the possibility that unexpected safety events may occur. The list of expected safety events is including in Section 1.4.1 and in the APP13007 Investigator's Brochure.

Risks Associated with the Corticosteroid Class		
Intraocular pressure (IOP) increase	
IOP will be monitored during the study.
 
The protocol excludes participation of subjects who may be at increased risk of steroid-induced IOP increase, eg. subjects with a history of raised IOP and subjects with IOP >30 mmHg at the POD1 pre-randomization assessment.
	
The toxicology studies with APP13007 indicate that there is a low risk of IOP increase during the 21 days of treatment.
 
Prolonged use of CP may result in glaucoma with damage to the optic nerve, defects in visual acuity and fields of vision.
 
An IOP ≥ 30 mmHg after randomization should be reported as an AE.

Potential Risk	Management	Comments
	
Section 9 includes stopping criteria for study drug due to IOP increase and criteria for initiation of IOP-lowering medication.
 
After Randomization, the management of IOP > 30 mmHg or IOP ≥ 24 mmHg AND an IOP increase ≥ 10 mmHg from pre-dose baseline is described in Section 9.4.2.
	
An IOP ≥ 24 mmHg AND an IOP increase ≥ 10 mmHg from pre-dose baseline should be reported as an AE.

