Cataracts	
The lens structure and posterior capsular opacification (POC) in the study eye will be monitored at each clinic visit throughout the study. The lens in the non-operated eye will be evaluated at Screening, EOS and Early Termination visits.
	
Based on data from studies of dermal products of CP, use of APP13007 may result in posterior subcapsular cataract formation in the non-operated eye. While the risk is likely to be small, this cannot be quantified because the extent of CP systemic exposure in humans following ocular instillation of APP13007 is not known.

Delayed Healing	
Subjects with thinning of the cornea or sclera are excluded because of the greater risk of perforations with the use of topical steroids.
 
Protocol includes stopping criteria for study drug if the Investigator, in consultation with the Study Medical Monitor, is concerned about delayed healing.
	
Use of APP13007 may delay healing after cataract surgery and increase the incidence of bleb formation.

Risk of Infection	
Subjects with on-going ocular bacterial, viral or fungal infections are excluded from the study.
 
Ocular infections occurring during the study should be assessed and treated appropriately.
 
The Investigator should discuss with the Study Medical Monitor whether to stop study drug if ocular infection occurs.
	
Use of APP13007 may suppress the host immune response and increase the hazard of ocular infections. This risk is likely to be low based on potential low systemic CP exposure and data from studies of other steroids products approved for the treatment of inflammation and pain after ocular surgery.

Hypothalamic-Pituitary-Adrenal	Monitor for symptoms and signs of reduced adrenal function	Systemic absorption of topical corticosteroids can produce

Potential Risk	Management	Comments

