4.3. Exclusion Criteria

Participants will be excluded if they meet any of the following criteria:

1. Have a known sensitivity or allergy to clobetasol propionate, corticosteroids, or any of the study medication's components including benzalkonium chloride and soybean lecithin
2. Have an ACC > 0 or any evidence of intraocular inflammation (e.g., flare) in either eye as found during the slit lamp examination at the Screening visit
3. Have a score > 0 on the Ocular Pain Assessment in either eye at the Screening visit
4. Have an immunosuppressive or autoimmune disease that in the opinion of the Investigator could affect intraocular inflammation or the normal healing process of the eye
5. Have active or chronic/recurrent ocular or systemic disease that is uncontrolled and would likely affect wound healing and/or resolution of inflammation after cataract surgery.
6. Have suspected or known malignancy or received antineoplastic therapy within the 12 months prior to the Screening visit. Note: subjects with basal cell carcinoma will not be excluded unless the Investigator believes that the condition has the potential to interfere with study procedures or analysis of results.
7. Use of treatments for macular degeneration including Eylea® (aflibercept), Avastin® (bevacizumab), and Lucentis® (ranibizumab)
8. Use of systemic or topical anti-inflammatory agents, analgesics/pain relievers (including opioids, narcotics, NSAIDS, aspirin, acetaminophen and other pain medications) or immunomodulating agents systemically or in either eye (including Lifitegrast (Xiidra)) from the washout period until the End-of-Study (EOS) visit.
Note: Medication for anesthesia and pain control at surgery are allowed on the day of surgery only. (See Section 5.4.2.)
9. Use of any of the prohibited medications (see Section 5.4.2) within a time period prior to surgery that is less than the minimum 'washout' period noted in the table.
[NOTE: These medications may not be used after randomization through the EOS visit.]
10. Have an intraocular pressure (IOP) < 5 mmHg or > 22 mmHg in either eye at the Screening visit.
11. Have a history of documented repeated elevated IOP
12. History of herpes keratitis in the study eye
13. Have active corneal abrasions or ulcers in the study eye
14. Have active or a history of chronic or recurrent inflammatory eye disease (e.g., iritis, scleritis, uveitis, iridocyclitis, rubeosis iridis) in the study eye

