25. Have a planned use of or use of femtosecond laser or any other ophthalmic surgical procedure (e.g., vitrectomy, relaxing incisions, iridectomy, conjunctival excisions, use of iris hooks or other iris dilators, etc.) in addition to the cataract extraction procedure via phacoemulsification and PCIOL implantation in the study eye
26. Have a planned use of or use anterior capsule staining for capsulorhexis (i.e., trypan blue) during cataract surgery
27. Have previously been enrolled in this clinical study, or have planned to participate in another clinical trial during the duration of this study

- 28. Have participated in another clinical study or received any investigational product within the past 28 days prior to the Screening Visit
- 29. Have any other condition that the Investigator determines should exclude the subject from the trial
- 30. Are an employee of the clinical site that is directly involved in the management, administration, or support of this study or are an immediate family member of the same.

[figure not shown]

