6.2.2. Postoperative Day 1 (POD1) – Day of Randomization

Subjects will return to the clinic for the next study visit on POD1 between 18 to 34 hours following conclusion of surgery on Day 0. This visit should be scheduled in the morning, as much as possible, to allow for administration of two doses of study drug during the day on POD1 for eligible subjects. The first dose of study drug is to be administered under supervision at the study site, and the second dose can be administered at home.

The site will review eligibility criteria (Section 4.2 and Section 4.3) to determine if the subject qualifies for randomization. If the subject meets all criteria, the subject will be randomized by site personnel using the EDC/IWRS system. The site should follow the

instructions provided in the Study Reference Manual (SRM) to enter appropriate subject data into the eCRF and randomize the subject. A study drug bottle number will be assigned to the subject based on the predetermined randomization by the EDC/IWRS system. All assessments and blood draw for safety labs and blood cortisol level on POD1 must be done prior to Randomization. The site should administer the first dose of study drug to the subject in the clinic before dispensing the assigned study drug bottle along with written dosing instruction and diary to the subject.

Study drug dosing/administration including handling bottle replacement, diary/dosing compliance and the list of treatments are presented in Section 5.1.2. Subjects are reminded to bring diary to each clinic visit in order for site staff to review dosing compliance. Note that study drugs in Part A will be administered BID for 21 days (POD1 to POD21), while in Part B, study drugs will be administered BID for the first 3 days and then QD thereafter for the duration of the treatment period in the study, i.e., for 11 days (POD4 to POD14).

6.2.3. PODs 1 through 15

All assessments will be performed as shown in the Schedule of Events (Table 2A and Table 2B).

Note that blood samples for safety laboratory assessments and cortisol level will only be collected in Part A. Also note that ocular assessments will be performed only in the operated, study eye at PODs 1, 4, 8, 15 and 22 visits in Part A and PODs 1, 4, 8 and 15 in Part B.

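### The risk mitigation plan says corneal or scleral thinning is excluded, but no eligibility criterion names it

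*Protocol*

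**What the plan says.** Protocol Section 1.4.1 gives the hazard, under delayed healing: "In those diseases causing thinning of the cornea or sclera, perforations have been known to occur with the use of topical corticosteroids". Table 3 gives the mitigation as a settled fact: "Subjects with thinning of the cornea or sclera are excluded because of the greater risk of perforations with the use of topical steroids".

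Eligibility is defined in Sections 4.2 and 4.3 and repeated in the Synopsis. Section 6.2.2 makes those sections the working test on the day of randomisation: "The site will review eligibility criteria (Section 4.2 and Section 4.3) to determine if the subject qualifies for randomization".

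Two exclusion criteria in Section 4.3 bear on the subject in general terms. Criterion 5 removes a subject with "ocular or systemic disease that is uncontrolled and would likely affect wound healing". Criterion 29 is the catch-all: "Have any other condition that the Investigator determines should exclude the subject from the trial". Section 1.4.1.2 lists contraindications. It opens with "APP13007, as with other corticosteroids, is contraindicated in the presence of active viral diseases of the cornea and conjunctiva" and goes on to mycobacterial and fungal eye disease; thinning is not among them.

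**The concern.** A risk table does not screen subjects; the eligibility list does. Table 3 describes the exclusion of thinning as already in place, so anyone reading the risk section, an IRB member for instance, would take the perforation risk as dealt with at entry. Site staff working through the numbered criteria on POD1 meet no such item.

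The stake is the safety of individual subjects. The protocol itself links topical corticosteroids to perforation where disease has thinned the cornea or sclera. Section 1.4.2 says this is the first administration of APP13007 to humans, and Section 1.2.3 describes the active ingredient as reportedly the most potent steroid. A subject admitted through the gap would also meet every numbered criterion, so the inclusion/exclusion listings in SAP Section 6.1 need not show the case.

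**Working it through.** No arithmetic beyond a count applies. The check is a comparison of texts.

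**Step 1. Are the lists complete?** The inclusion criteria run 1 to 9 and the exclusion criteria 1 to 30 in both places, with no numbering gap or redaction. The amendment log's entries on the exclusion criteria concern renumbering, lifitegrast and antibiotic wording. So neither missing text nor superseded text explains the omission.

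**Step 2. Does any criterion name thinning?** 9 + 30 = 39 criteria; 0 of 39 name thinning of the cornea or sclera, in the Synopsis or in Section 4. The word appears for these tissues only in Section 1.4.1 and Table 3.

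**Step 3. Which criteria reach it indirectly?**

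| Exclusion criterion | What it removes | What limits it as cover for thinning |
|---|---|---|
| 4 | Immunosuppressive or autoimmune disease | Investigator must think it could affect inflammation or healing |
| 5 | Disease likely to impair healing or resolution of inflammation | Only if uncontrolled |
| 12 | Any history of herpes keratitis | That cause only |
| 13 | Corneal abrasion or ulcer | Only if active |
| 14 | Chronic or recurrent inflammatory eye disease, including scleritis, active or in the history | Inflammatory causes only |
| 15 | Acute external infection, ocular tuberculosis, intraocular infection, some lid disease | Infective or lid causes only |
| 16 | Corneal dystrophy, dysthyroid ophthalmopathy | Those diagnoses only |
| 19 | Corneal or retinal surgery | Only within 6 months before Screening, or planned during the study |
| 21 | Trauma with visible scarring or deformity | Investigator must think it may matter |
| 29 | Anything else | Wholly at the investigator's discretion |

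Criteria 12 to 16, 19 and 21 apply to the study eye, which is the eye that receives the drug.

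**Step 4. What is left?** Thinning that is not due to active ulceration, inflammatory disease, infection, dystrophy, recent surgery or qualifying trauma, is not tied to uncontrolled systemic or ocular disease, and is not excluded by the investigator under criterion 29. Table 3 says such a subject is out; Sections 4.2 and 4.3 do not.

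**Step 5. How many subjects?** The documents give no prevalence of thinning, so no count can be derived.

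**The case against.** The best reply is that the risk is described at the level of diseases that cause thinning, and the criteria work at that level too. Nine specific criteria reach such diseases. Criterion 14 covers a past history of chronic or recurrent scleritis as well as active disease, and criterion 12 covers any past herpes keratitis. An ophthalmologist who saw marked thinning at the slit lamp would very probably use criterion 29. This stands, and it is why the gap is modest. It does not close the gap: Table 3 asserts a categorical exclusion, and criterion 29 offers discretion.

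A second reply concerns detection. Table 3 is part of the protocol, so enrolling such a subject contradicts the protocol even if no numbered criterion is breached. SAP Section 6.2 counts a deviation as major if it could affect subject safety, and Listing 16.2.2.4 gives the details. That also stands: the eligibility listings are not the only route by which a case could surface, although someone would have to recognise it as a deviation first.

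A reader might infer that thinning is a lone lapse in a table that otherwise matches the criteria exactly. The documents do not support that. Table 3 speaks of "subjects with a history of raised IOP and subjects with IOP >30 mmHg at the POD1 pre-randomization assessment", while exclusion 11 is narrower: "Have a history of documented repeated elevated IOP". The infection statement in Table 3 names no eye, while criterion 15 is confined to the study eye. The hypersensitivity row is partly redacted and cannot be fully compared. Table 3 paraphrases eligibility loosely in several rows; thinning is the case where no specific counterpart can be found.

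**Conclusion.** The inconsistency is real and should be corrected. The protocol states an exclusion for perforation risk that its operative eligibility list does not contain: 0 of 39 criteria name it.

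Its reach is limited to the residual group in Step 4, of unknown size. A reader might infer that subjects at risk of perforation were left unprotected, or that some were in fact enrolled. Neither follows: the adjacent criteria remove many of the causes, the investigator can exclude the rest, and nothing in the documents shows that any such subject entered.

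No efficacy or safety estimate is affected. Efficacy is analysed in all randomised subjects and safety in all who were dosed, so the wording of this criterion alters neither population's definition. The SAP appendix has also dropped the per-protocol analyses.

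The conclusion rests on two assumptions: that sites decide eligibility on Sections 4.2 and 4.3, as Section 6.2.2 tells them to, and that no study document outside the protocol and SAP adds the criterion.

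**What to change.** Add one exclusion criterion to the Synopsis and to Section 4.3: *corneal or scleral thinning in the study eye, in the Investigator's judgement on slit-lamp examination*. Tying it to the slit lamp matters, because no corneal-thickness measurement is scheduled and none need be added; slit-lamp biomicroscopy is already done at Screening and on POD1. The gain is an explicit prompt and a consistent protocol, not a measured threshold.

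The cost is one line in two places and slightly narrower eligibility. Introducing it for Part B alone would not disturb any comparison, since SAP Section 5.1.1 analyses each part separately. Rewording Table 3 instead would restore consistency but give up the stated safeguard.

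Enrolment may well have closed: the SAP appendix reports 132 subjects against about 42 + 84 = 126 planned. In that case, check the ocular history (Listing 16.2.4.2) and the slit-lamp findings (Listing 16.2.9.3) for thinning, report any case as a deviation from the stated risk mitigation plan, and carry the criterion into the next protocol. This check can miss cases, because Section 7.3.3 lists no thinning item and SAP Section 6.4 refers to significant history only. A clean result would be reassuring but not conclusive.

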2. STUDY OBJECTIVES AND ENDPOINTS

The objectives and corresponding study endpoints are depicted in Table 4 below.

Table 4: Study Objectives and Endpoints

Objectives	Endpoints
The primary safety objective of this study is to investigate the safety and tolerability of APP13007 versus corresponding matching vehicle placebo for the treatment of inflammation and pain through POD22 in Part A and POD15 in Part B after cataract surgery.	
• Early Treatment Diabetic Retinopathy Study (ETDRS) Best corrected Visual Acuity by pinhole method• Slit-lamp biomicroscopy• Change from baseline to each post-surgery visit in ocular signs:
○ Corneal edema○ Ciliary flush○ Bulbar conjunctival injection• Dilated indirect ophthalmoscopy• Intraocular pressure (IOP)• Adverse event (AE) monitoring• Clinical chemistry and hematology parameters (Appendix A)• Blood cortisol concentrations
The primary efficacy objective of this study is to investigate the preliminary efficacy of APP13007 versus matching vehicle placebo for the treatment of inflammation and pain through POD15 after cataract surgery.	
• Anterior chamber cell (ACC) count at POD15• Pain grade on POD15
The secondary efficacy objective of this study is to compare the effects on markers of inflammation and pain and visual acuity between active APP13007 and matching vehicle placebo for each dose strength and frequency.	
• Anterior chamber cell (ACC) count at PODs 4, 8, and 22/EOT (Part A) and PODs 4 and 8 (Part B).• Pain grade on PODs 4, 8, and 22/EOT (Part A) and PODs 4 and 8 (Part B)• Anterior chamber flare (ACF) grade on PODs 4, 8, 15 and 22/EOT (Part A) and PODs 4, 8 and 15/EOT (Part B)• Use of rescue medication prior to each visit• Proportion of subjects with ACC count = 0 at PODs 4, 8, 15 and 22/EOT (Part A) and PODs 4, 8 and 15/EOT (Part B) without receiving rescue medication;• Proportion of subjects who are pain-free at PODs 4, 8, 15 and 22/EOT (Part A) and PODs 4, 8 and 15/EOT (Part B)

	
15/EOT (Part B) without receiving rescue medication;
 
• Proportion of subjects with flare grade = 0 at PODs 4, 8, 15 and 22/EOT (Part A) and PODs 4, 8 and 15/EOT (Part B) without receiving rescue medication• Visual acuity (ETDRS Best corrected Visual Acuity by pinhole method)
--	---

3. STUDY DESIGN

3.1. Study Design Overview

This is a Phase 2a, 2-part study (designated Parts A and B) that will evaluate APP13007 dose strength and dosing frequency in a randomized double-masked fashion for comparison to the respective matching vehicle placebo. Part A (0.05% BID regimen) will be conducted first.

Part A:

Approximately 42 subjects who experience postoperative inflammation on the first day following routine, uncomplicated, cataract surgery and who meet all eligibility criteria will be randomized to one of two study treatments in an approximate 1:1 ratio to receive either Treatment 1 or Treatment 2 in a double-masked fashion (with sufficient number of subjects enrolled to allow approximately a total of 40 subjects, 20 per treatment, to complete dosing and study procedures through POD15).

- Treatment 1: 1 drop 0.05% APP13007 BID (morning and evening) for 21 days to the operated eye
- Treatment 2: 1 drop matching vehicle placebo BID (morning and evening) for 21 days to the operated eye

Following completion of the POD22 visit (i.e., End-of-Treatment (EOT) visit) for all subjects at all sites in Part A, Part B (0.05% and 0.1% along with respective matching vehicle placebo, BID regimen for 3 days followed by QD regimen for 11 days) will be opened for randomization.

See Section 3.3 for a detailed description of the process for progressing from Part A to Part B.

Part B:

Approximately 84 subjects who experience postoperative inflammation on the first day following routine, uncomplicated, cataract surgery and who meet all eligibility criteria will be randomized to one of four study treatments in an approximate 1:1:1:1 ratio to receive Treatment 3, Treatment 4, Treatment 5 or Treatment 6 in a double-masked fashion (with sufficient number of subjects enrolled to allow approximately a total of 80 subjects to complete dosing and study procedures, approximately 20 per treatment, through POD15):

- Treatment 3: 1 drop 0.05% APP13007 BID (morning and evening) for 3 days (PODs 1, 2 and 3) followed by 1 drop 0.05% APP13007 QD (morning) for 11 days (PODs 4 through 14) to the operated eye
- Treatment 4: 1 drop 0.05% matching vehicle placebo (0.05% APP13007 vehicle) BID (morning and evening) for 3 days (PODs 1, 2 and 3) followed by 1 drop

matching vehicle placebo QD (morning) for 11 days (PODs 4 through 14) to the operated eye

- Treatment 5: 1 drop 0.1% APP13007 BID (morning and evening) for 3 days (PODs 1, 2 and 3) followed by 1 drop 0.1% APP13007 QD (morning) for 11 days (PODs 4 through 14) to the operated eye
- Treatment 6: 1 drop 0.1% matching vehicle placebo (0.1% APP13007 vehicle) BID (morning and evening) for 3 days (PODs 1, 2 and 3) followed by 1 drop matching vehicle placebo QD (morning) for 11 days (PODs 4 through 14) to the operated eye

Alternatives to Planned Dosing Regimens in Part B: Based on the results from Part A, Part B may only enroll subjects into two of the treatment arms (either Treatments 3 and 4 or Treatments 5 and 6) or alternatively as shown in Section 3.3. Sites will be notified of a change in treatments in a communication when announcing the opening of randomization for Part B (Section 3.3). In addition, the IRB and FDA will be notified of any change in the planned treatments in Part B of the study.

